### Routine procedures for all patients:

Patients head will be positioned in optimal position. Head- end of the operating table elevated to 20 degrees to improve pulmonary reserve. A twitch monitor is placed pre induction.

Pre oxygenation will be achieved by providing supplemental oxygen through mask with either 3 minutes of tidal volume breaths/ 8 vital capacity breaths.

Standard induction technique for both groups. All patients will be induced with standard induction doses of lidocaine 1- 1.5 mg/kg, fentanyl 1-2 mcg/kg and propofol 1-2 mg/kg followed with saline flush. After loss of consciousness is confirmed, patients will be given Succinyl choline 1.5 mg/kg total body weight (TBW) for paralysis. Apneic oxygenation will be continued after induction. Ventilation will not be performed during this time unless desaturation with spo2 less than 90 % is observed .Loss of Train of four (TOF)will be checked to confirm paralysis, and the provider will proceed with intubation.

A video laryngoscope (glidescope) with style will be used for intubation of all patients. Time to intubate (TTI) will be calculated by an independent provider not directly involved in research study. If intubation is unsuccessful by primary provider , further attempts by any other provider will be documented separately. If difficulty

to intubate is deemed secondary to intubation box, it will be removed immediately.

Intubation procedure will be performed by provider with more than 3 years of

experience and has performed at-least 3 intubations with intubation barrier box with

patients.

Timing of all events will be performed by independent provider.

Other data points calculated.

Induction time – loss of spontaneous ventilation to placement of ETT.

Episode of hypoxia defined by spo2 < 90 %

Time duration of bag –mask ventilation if needed.

Source record: Electronic medical record

Long-term data collection: None

Withdrawal of participants:

Unanticipated difficult intubation as described by > 3 attempts by experienced

provider.

Patients in the study will be excluded secondary to any equipment malfunction

or unforeseen delays not related to patient care.

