## Risk to participants:

By design, there is a minimal risk to the participants in this study. The intubation barrier box could be a source of claustrophobia to the patient which will be mitigated by use of anxiolytics. The intubation box will be removed if it creates any difficulty in intubation.

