# Sharing of individual participant data with other researchers

There is no plan to make individual participant data collected in this study available to other researchers. Data will be fully de-identified before sharing.

DATA SHEET
Pre-op
Age:
Sex:
ASA:
BMI:
Airway assessment:
METS / functional status:
Cardio –pulmonary status:
Previous known difficult airway record:
Medical history:
GERD, OSA, H/O MI, CHF, SEVERE COPD, HOME OXYGEN, RECENT
COVID INFECTION
Surgical history:
H/O neck fusion

Labs:
ВМР
ЕСНО
INTRAOP
Use of peri op anxiolytics
Induction medications
Apnea time
Time of intubation
Subjective difficulty in intubation
Need for bag - mask ventilation
Episode of hypoxia as defined by SpO 2 < 90 %
POST OP: Subjective patient experience
Peri- operative complications if any.

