## Statistical analysis plan:

#### Sample size calculation

Sample size calculation was done by using the two means equation in the Power and Sample Size Calculation program (Dupont and Plummer, 1990). Based on a study by Teoh et. al., (2019), the mean of intubation time for Glidescope was 31.2 seconds and Airway Scope was 20.6 seconds. A clinically significant effect of 10 seconds would be of interest. The two-tailed hypothesis testing concluded that each group needed 36 subjects to achieve a power of 80%, with an error rate of 5%. A total of 90 subjects will be enrolled in this study with an estimated dropout rate set at 20%, 45 subjects will be enrolled in each group.

Suggested citation for Power and Sample Size Software:

Dupont WD, Plummer WD: 'Power and Sample Size Calculations: A Review and Computer Program', Controlled Clinical Trials 1990; 11:116-28.

Reference article:

It is a standard practice to include a dropout rate of 20% for clinical trials so that the power of the study will not be affected by dropouts, missing data and other study deviations (https://online.stat.psu.edu/stat509/node/47/).

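### Randomised patients can be withdrawn after more than three intubation attempts or excluded for equipment malfunction, and no analysis set keeps them in the TTI comparison

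*Protocol*

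**What the plan says.** Patients are randomised after verbal consent and before induction (Protocol, Procedures involved in Human research). Under Routine procedures for all patients, the Withdrawal of participants list then gives two rules:

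- "Unanticipated difficult intubation as described by > 3 attempts by experienced" provider;
- "Patients in the study will be excluded secondary to any equipment malfunction", continued on the next line as "or unforeseen delays not related to patient care".

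The same section says that if the primary provider fails, "further attempts by any other provider will be documented separately". If difficulty is attributed to the box, the instruction is that "to intubate is deemed secondary to intubation box, it will be removed immediately" applies; Risk to participants repeats it: "The intubation box will be removed if it creates any difficulty in intubation". Box removal is not itself a ground for withdrawal.

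Primary TTI runs from loss of twitch to end-tidal CO2 confirmation (Protocol, Study end points and Primary end point; SAP, Primary endpoint). The SAP tests it with a one-sided t-test at p < 0.05 against a 15 s margin. It does not say who is analysed and repeats neither withdrawal rule. The protocol also plans a CONSORT flow diagram and a 20% dropout allowance.

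**The concern.** The attempts rule is tied to the outcome. A patient who needs more than three attempts will tend to have one of the longest TTIs, and that is the patient who is withdrawn. In a non-inferiority trial, losing long times from the experimental arm favours the claim under test.

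The malfunction rule may act unevenly, because the box exists in one arm only. The closing qualifier about patient care may limit only the delays or the malfunctions as well, so the text does not clearly keep box malfunctions in.

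Two linked gaps make this harder to repair afterwards:

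- Recording another provider's attempts separately leaves open whether that time counts in TTI, so even a retained patient's value is unsettled.
- The intraoperative data sheet has an entry for "Subjective difficulty in intubation" but none for number of attempts, box removal, malfunction or reason for exclusion. The electronic record may hold these.

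The SAP's first-attempt percentage is exposed in the same way. With assumed counts, 40/45 = 88.9% becomes 40/44 = 90.9% when one patient leaves the denominator.

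**Working it through.** **1. The plan's own sample size, to obtain an SD.** The protocol states: "The two-tailed hypothesis testing concluded that each group needed 36 subjects to achieve a power of 80%, with an error rate of 5" per cent, for a 10 s difference. No SD is given. Solving n = 2·SD²·(1.960 + 0.842)²/10² for n = 36:

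SD = 10 / (2.802 × √(2/36)) = 15.1 s (14.9 s with the t distribution).

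The enrolment figure reproduces: 36/(1 − 0.20) = 45 per arm. I use SD 15 s and 45 per arm.

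**2. Assumptions, because the documents give no event rates or times.** Control TTI without events is lognormal with mean 31.2 s (the Glidescope mean in the sample size section). A share p of an arm has TTI = L. The remaining box patients are shifted so that the true all-randomised difference is exactly 15 s, the margin. The test is a pooled one-sided t-test at 5%, with 40,000 simulated trials per scenario.

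**3. Expected difference after withdrawal.**

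- Control mean, all randomised: C = (1 − p_c)·31.2 + p_c·L
- Box mean, kept patients: B = (C + 15 − p_b·L)/(1 − p_b)
- Analysed difference: B − 31.2

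Example, 2% box and 0% control, L = 120 s: B = (31.2 + 15 − 2.4)/0.98 = 44.7 s, so the analysed difference is 13.5 s although the truth is 15 s.

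**4. False non-inferiority rate, L = 120 s.**

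| Box / control rate | Analysed difference after withdrawal | Withdrawn | All kept |
|---|---|---|---|
| none | 15.0 s | 5.0% | 5.0% |
| 1% / 0.5% | 14.7 s | 6.1% | 5.1% |
| 1% / 0% | 14.3 s | 8.2% | 5.6% |
| 2% / 1% | 14.4 s | 7.6% | 5.3% |
| 2% / 0% | 13.5 s | 12% | 6.0% |
| 5% / 2% | 13.0 s | 16% | 5.4% |
| 2% / 2% | 15.3 s | 4.0% | 4.7% |
| 0% / 2% | 16.8 s | 1.3% | 3.9% |

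The last two differences follow from step 3 with C = 0.98 × 31.2 + 0.02 × 120 = 32.976 s: (47.976 − 2.4)/0.98 − 31.2 = 15.3 s, and 47.976 − 31.2 = 16.8 s.

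**5. Sensitivity (withdrawn against kept).**

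- L = 90 s: 5.4% against 5.0% (1%/0.5%), 6.6% against 5.1% (1%/0%), 8.6% against 5.2% (2%/0%), 9.5% against 5.1% (5%/2%).
- 2%/0% at 120 s: SD 10 s gives 18% against 7.5%; SD 20 s gives 9.9% against 5.4%.

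**6. How often the rule would bite.** The chance of no box-arm event is 0.99^45 = 64% at a 1% rate and 0.98^45 = 40% at 2%.

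**The case against.** **Removal from the analysis is inferred.** The attempts rule sits under a withdrawal heading; only the malfunction and delay sentence says excluded. The SAP repeats neither rule and could be read as analysing everyone with a TTI. This stands as a limit on certainty. But with both readings open, the choice could be made after the times are known.

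**The mechanism may be weak.** The box is to be removed at once if it causes difficulty, so cases reaching a fourth attempt may be mainly anatomical, which randomisation balances on average. Known or anticipated difficult airways and BMI > 35 are excluded, a video laryngoscope is used throughout and operators are experienced. This stands: rates are probably low, direction is unknown, and at 1%/0.5% the inflation is about one percentage point.

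**The malfunction limb is ambiguous, and no box malfunction is described.** True; the attempts rule carries no such qualifier and supports the point by itself.

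**Other provisions help.** A CONSORT diagram would normally show losses by arm, but showing them does not return them to the comparison. The 20% allowance is justified only as protecting power and does not address bias.

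**A lighter remedy would do:** define the analysis sets and add an all-randomised sensitivity analysis. That would help, but it leaves the primary result resting on a selection made by the outcome process.

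**Conclusion.** The concern holds and should be fixed, with moderate confidence. The protocol states post-randomisation removal rules, one of them tied directly to the primary endpoint, and nothing in either document keeps the affected patients in the TTI comparison.

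The bias is conditional. It favours non-inferiority only if the removed cases are commoner or longer with the box. Within the assumed scenarios of that kind at SD 15 s, the false non-inferiority rate with withdrawal runs from 5.4% (1%/0.5% at 90 s) to 16% (5%/2% at 120 s), against 5.0% to 6.0% with everyone kept. The low end is the more plausible for this population. These figures rest on assumed rates and durations, a lognormal shape and an SD recovered from the sample size statement.

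**What to change.** **Change to make**

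- Primary analysis: all randomised patients who are induced, in their assigned group. More than three attempts, box malfunction and box removal do not remove a patient from the analysis; the last two are reported as box-arm events.
- TTI: state that it runs to final end-tidal CO2 confirmation across all attempts and providers, with later attempts also recorded separately. This reconciles the endpoint definition with the procedures text.
- Exclusions: only failures that can occur in either arm and make TTI unmeasurable (for example twitch monitor or capnograph failure), and delays unrelated to the intubation. Decide them without knowledge of TTI and report them by arm and reason.
- Never-intubated patients: state in advance how they count, for example a fixed worst value varied in a sensitivity analysis, with a rank-based analysis as support.
- Keep the analysis under the current exclusions as a sensitivity analysis.
- Add data-sheet fields for attempts, box removal, malfunction and exclusion reason.

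Clinical handling of the airway is unchanged.

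**Cost**

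- Wording, four fields, and continued timing in a few patients. TTI would include a second provider's time where one takes over.
- Precision (events at 120 s): the standard error of the difference rises from 3.17 s to 3.35 s (1%/0%), 3.52 s (2%/0%) or 4.40 s (5%/2%), that is by about 6%, 11% and 39%. Power at a true difference of 5 s falls from 93% without events to 88%, 84% and 70%.
- With skewed data the t-test runs slightly above 5% (5.6% at 1%/0%, 6.0% at 2%/0%).
- The fixed value matters. Against a box mean of 31.2 + 15 = 46.2 s, one never-intubated box patient adds (180 − 46.2)/45 = 3.0 s, or (300 − 46.2)/45 = 5.6 s.
- The rank-based test examines a 15 s shift, not the mean. When the mean difference is 15 s it passes in 7.1% (1%/0%) and 10.6% (2%/0%) of trials, so it can support the primary analysis but not replace it.

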## Risk to participants:

By design, there is a minimal risk to the participants in this study. The intubation barrier box could be a source of claustrophobia to the patient which will be mitigated by use of anxiolytics. The intubation box will be removed if it creates any difficulty in intubation.

#### Provisions to maintain confidentiality of the data:

Measures will be taken to protect patient confidentiality in accordance with HIPAA guidelines. Patient's names will not be used on the data collection sheet. Medical record numbers will be used on the data collection sheet. Once data collection has been completed, the MRN will be removed from the datasheet and the patients will be numbered consecutively. No patient names or medical record numbers will be published. Descriptive statistics will be used to summarize our objectives. Data will be stored as an electronic file on a password-protected computer and will only be available to primary and co-investigators.

## Potential direct benefit to patients:

There are no direct benefits to patients, but they may be making a contribution to the scientific knowledge, and help create a model for correcting deficiencies, if present. Information demonstrated by the box will help provide additional safety to health care personnel.

## **Participant Compensation/Cost**

There will be no payment or costs to subjects.

## **Vulnerable populations:**

Children will be excluded from the study. Pregnant women and prisoners will not be specifically targeted for chart review.

#### **Consent process:**

Due to the prospective design of the study, a consent will be taken. Consent will be obtained verbal rather than written. A waiver of consent documentation is requested from the IRB because the research presents no more than minimal risk of harm to subjects, and the research involves no procedures for which written consent is normally required outside of the research context and is part of routine anesthesia patient care. The verbal consent will take place during pre- operative assessment prior to the surgery by a member of research team .

## Sharing the results with the participants:

There are no plans to directly share data or results with the participants.

# Sharing of individual participant data with other researchers

There is no plan to make individual participant data collected in this study available to other researchers. Data will be fully de-identified before sharing.

DATA SHEET
Pre-op
Age:
Sex:
ASA:
BMI:
Airway assessment:
METS / functional status:
Cardio –pulmonary status:
Previous known difficult airway record:
Medical history:
GERD, OSA, H/O MI, CHF, SEVERE COPD, HOME OXYGEN, RECENT
COVID INFECTION
Surgical history:
H/O neck fusion

Labs:
ВМР
ЕСНО
INTRAOP
Use of peri op anxiolytics
Induction medications
Apnea time
Time of intubation
Subjective difficulty in intubation
Need for bag - mask ventilation
Episode of hypoxia as defined by SpO 2 < 90 %
POST OP: Subjective patient experience
Peri- operative complications if any.

## Statistical analysis plan:

#### Sample size calculation

Sample size calculation was done by using the two means equation in the Power and Sample Size Calculation program (Dupont and Plummer, 1990). Based on a study by Teoh et. al., (2019), the mean of intubation time for Glidescope was 31.2 seconds and Airway Scope was 20.6 seconds. A clinically significant effect of 10 seconds would be of interest. The two-tailed hypothesis testing concluded that each group needed 36 subjects to achieve a power of 80%, with an error rate of 5%. A total of 90 subjects will be enrolled in this study with an estimated dropout rate set at 20%, 45 subjects will be enrolled in each group.

Suggested citation for Power and Sample Size Software:

Dupont WD, Plummer WD: 'Power and Sample Size Calculations: A Review and Computer Program', Controlled Clinical Trials 1990; 11:116-28.

Reference article:

It is a standard practice to include a dropout rate of 20% for clinical trials so that the power of the study will not be affected by dropouts, missing data and other study deviations (https://online.stat.psu.edu/stat509/node/47/).

#### **Randomization:**

Sealed Envelope Ltd. 2019. Simple randomisation service. [Online] Available from: https://www.sealedenvelope.com/simple-randomiser/v1/ [Accessed 6 May 2020]. Randomization will remain concealed from the researchers until the time of the verbal informed consent.

# **CONSORT flow diagram:**

Participants will be tracked using a CONSORT flow diagram.

# **Primary end point:**

Calculating time to intubate (TTI) which is defined as time duration from loss of twitch to confirmation of end tidal CO 2. Comparing time to intubate (TTI) between study and control group using a t-test to compare means.

Non-inferiority margin set at 15 seconds. Non- inferiority hypothesis (H  $_0$ : Mean TTI diff  $\geq$ 15 s, H  $_A$ : Mean TTI diff < 15 s).

Statistical Analysis Plan

Date November 20, 2024

Title: Time to Adapt in the Pandemic Era: A Prospective Randomized Study Comparing Time to Intubate With and Without the Barrier Box

Principal Investigator: [name]

Sub-Investigators: [name], [name], [name]

Research Site: Guthrie Robert Packer Hospital, Department of Anesthesiology

National Clinical Trial Number: NCT04411056

Sample size calculation

Sample size calculation was done by using the two means equation in the Power and Sample Size Calculation program (Dupont and Plummer, 1990). Based on a study by Teoh et. al., (2019), the mean of intubation time for Glidescope was 31.2 seconds and Airway Scope was 20.6 seconds. A clinically significant effect of 10 seconds would be of interest. The two-tailed hypothesis testing concluded that each group needed 36 subjects to achieve a power of 80%, with an error rate of 5%. A total of 90 subjects will be enrolled in this study with an estimated dropout rate set at 20%, 45 subjects will be enrolled in each group.

Suggested citation for Power and Sample Size:

Dupont WD, Plummer WD: 'Power and Sample Size Calculations: A Review and Computer Program', Controlled Clinical Trials 1990; 11:116-28.

Reference article;

It is a standard practice to include a dropout rate of 20% for clinical trials so that the power of the study will not be affected by dropouts, missing data and other study deviations (https://online.stat.psu.edu/stat509/node/47/).

May 5, 2020 Statistical Consultant KV

The study plans to enroll approximately 72 subjects to two groups with 36 subjects in each group. This sample size is based on the estimated time difference of 10 seconds between intubation times with and without the box. (Protocol April 30, 2020)

Randomization:

Subjects will be randomized by block randomization. Randomization will be done by a random number generated computer program by someone not involved in the research. The randomization schedule will be placed in sealed envelopes to be concealed from the researcher until time of verbal consent.

Sealed Envelope Ltd. 2019. Simple randomisation service. [Online] Available from: https://www.sealedenvelope.com/simple-randomiser/v1/ [Accessed 6 May 2020].

Statistical Software

R 3.5.3 software will be used for statistical analysis.

Non-Inferiority Study Design

Hypothesis

Use of the barrier box prolongs the mean TTI by more than 15 s compared to a control group with no barrier box

HO: Mean TTI changes with barrier box

HA: Mean TTI does not change with barrier box

Non-inferiority margin: Our research team decided to use 15 s as non-inferiority margin. The premise of our non-inferiority study is to compare the mean TTI and infer if the additional time taken for airway manipulation with a barrier box is within acceptable non-inferiority margin between the means of both the groups (Box vs No Box). Non-inferiority margin of 15 s is considered acceptable while comparing airway manipulation in both the groups based on our clinical experience and pilot study data. Our literature review showed that this non-inferiority margin ($\Delta = 15$ s) would be within safe period of apnea tolerated by most patients (Moon et.al.)

Baseline data

Descriptive statistics for baseline demographics will include:

- Age in years- mean (standard deviation)
- BMI mean (standard deviation)
- Sex (male or female) frequency, number of participants
- American Society of Anesthesiology (ASA) Physical Status frequency, number of participants. ASA Physical Status is a classification system to assess a patient's preanesthesia medical co-morbidities, and helps predict perioperative risk when used with other risk factors such as frailty, level of deconditioning and type of surgery.
 - \circ ASA 1 a normal healthy patient
 - \circ ASA 2 a patient with mild systemic disease
 - ASA 3 A patient with severe systemic disease
 - The study will exclude patients who are ASA 4 (a patient with severe systemic disease that is a constant threat to life) or ASA 5 (a moribund patient who is not expected to survive without the operation).

Continuous variables of age and body mass index (BMI) will be reported as mean and standard deviation. Categorical variables of Gender (Sex) and ASA Physical Status will be reported in frequency tables.

For continuous variables, the two groups ("barrier box" or "no barrier box") will be compared using unpaired two-sample t-tests, if data meets assumptions for normally distributed data within each group and homogeneity of variances (equal variance between groups) For categorical variables, the two groups ("barrier box" or "no barrier box") at baseline will be compared using chi-square test of independence.

Primary endpoint

The primary end point is time to intubate (TTI) in seconds, from loss of twitch to confirmation of end tidal carbon dioxide.

TTI will be collected by an independent provider (registered nurse) not directly involved in airway management. The TTI is used as an outcome measure as it is an objective variable that can be measured and helps us in assessment of airway manipulation with a barrier box. We plan to use objective end points to eliminate inter- observer variability.

For the primary endpoint, mean TTI and 95% confidence intervals will be assessed and compared in the two groups, "barrier box" and control with "no barrier box".

An unpaired two-sample single-sided t-test will be used to test our non- inferiority hypothesis. The TTI of the barrier box group is expected to be higher than the mean TTI of control the group. Analysis will include two independent sample comparison of means using one sided t-test in R.

The t-test will be done based on assumptions that the sample has no dependence between subjects in the control group and the barrier box group. Similar variance in both the groups will be confirmed by Levine's test. With the sample size > 30, samples are expected to be from a population with a normal distribution. Results will be considered statistically significant when p < 0.05.

If the difference of the mean TTI between the groups is less than the non-inferiority margin of 15seconds, then the null hypothesis will be rejected.

Secondary endpoints and statistical analysis include:

- Attempts at intubation
 - o assessed as frequency (percentage) of patients intubated on first attempt.
- Need for bag mask ventilation (yes or no) during induction, defined as the time taken from propofol bolus to loss of twitches measured with a peripheral nerve stimulator.
 - assessed as frequency (number) of patients.
- Lowest oxygen saturation during induction (Lowest peripheral capillary oxygen saturation during induction, defined as the time taken from propofol bolus to loss of twitches measured with a peripheral nerve stimulator.
 - assessed as mean and standard deviation
- Induction time defined as the time taken from propofol bolus to loss of twitches measured with a peripheral nerve stimulator.
 - o assessed as mean (in seconds) and 95% confidence intervals

For continuous variables, the two groups ("barrier box" or "no barrier box") will be compared using unpaired two-sample t-tests, if data meets assumptions for normally distributed data within each group and homogeneity of variances (equal variance between groups)

For categorical variable, the two groups ("barrier box" or "no barrier box") will be compared using chi-square test of independence.

Airway assessment data will be collected for the two groups ("barrier box" or "no barrier box") as frequency data (number of patients) and will include:

- Mallampati score (scale of 0 to 4) used to assess and prepare for possible difficult intubation of participants who score high. Lower scores are less likely to have a difficult intubation, and higher scores are more likely to have a difficult intubation.
- Number of patients will be assessed in both groups for each of these classes:
 - Mallampati 0 (Any part of the epiglottis is visible)
 - Mallampati 1 (soft palate, uvula, and pillars are visible)
 - Mallampati 2 (soft palate and uvula are visible)
 - Mallampati 3 (only the soft palate and base of the uvula are visible)
 - Mallampati 4 (only the hard palate is visible)
- Thyromental Distance (TMD) > 3 finger breadth
 - TMD is the distance from the thyroid notch to the chin when the head is extended. TMD is used to assess and prepare for possible difficult intubation of participants who are less than or equal to 3 finger breadth. A distance of greater than 3 finger breadth may be less likely to have a difficult airway or airway constriction

Number of patients with TMD > 3 finger breadth will be assessed in both groups

- Inter incisor distance > 3 finger breadth
 - Inter incisor distance is the distance between the upper and lower teeth of the open mouth of a patient. Inter incisor distance is used to assess and prepare for possible difficult intubation of participants who are less than or equal to 3 finger breadth. A distance greater than 3 finger breadth may be less likely to have a difficult airway or airway constriction

Number of patients with Inter incisor distance > 3 finger breadth will be assessed in both groups.

- Neck range of motion (Full or Restricted)
 - Neck range of motion is the degree of movement in the neck how much the head can flex (bend forward), extend (tilt backwards), and rotate side to side. Full range of motion is less likely for a difficult airway or airway constriction than Restricted range of motion.

Number of patients with Neck range of motion (categorized as full or restricted) will be assessed in both groups.

For these airway assessment categorical variables, the two groups ("barrier box" or "no barrier box") will be compared using chi-square test of independence.

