**Study Timelines:** 

Individual subjects participation is limited to time spent in operating room

Duration for enrolling all participants: 2 months

Estimated date to complete study: 4 months

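### The one-sided 5% level and the revised secondary endpoints appear only in a SAP dated about four years after planned completion, and are not shown to be pre-specified

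*SAP*

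**What the plan says.** **Dates.** The SAP title block reads "Date November 20, 2024". Its sample size section refers to "Protocol April 30, 2020" and signs off the sizing with "May 5, 2020 Statistical Consultant". The protocol, under Study Timelines, gives "Duration for enrolling all participants: 2 months" and "Estimated date to complete study: 4 months", with participation confined to the operating room. The SAP is written in the future tense. It contains no version history, list of changes from the protocol, data-lock date or statement about when data were first accessed.

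**Primary test.** The protocol names a t-test without saying whether it is one- or two-sided. Its Primary end point section at the end adds a 15 s margin and a directional hypothesis (null: difference of 15 s or more) but no error level for that test. The sizing is two-tailed at 5%. The SAP is the only place that states sidedness for the non-inferiority test: "An unpaired two-sample single-sided t-test will be used to test our non- inferiority hypothesis", with significance at p < 0.05.

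**Secondary endpoints.** The protocol lists four under Study end points. The SAP also lists four, under Secondary endpoints, but they are mostly different; the working sets them side by side.

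**The concern.** A non-inferiority conclusion is read as confirmatory on the understanding that the error level and endpoint set were fixed before results by arm could be seen. Here the only document that fixes the one-sided 5% level and the revised secondary list is dated long after the trial was due to finish, and nothing in it ties those choices to an earlier date.

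The secondary list matters more than the test level. The dropped and narrowed items are the ones most likely to show harm or difficulty from working through a box: the provider's rating of difficulty, how long bag-mask ventilation lasted, and whether the patient fell below 90% saturation. If only the SAP list is reported as planned, a reader cannot tell a genuine absence of difference from one produced by the choice of endpoint.

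**Working it through.** **1. Timing.** 30 April 2020 plus 4 months is about 30 August 2020. From there to 20 November 2024 is 4.2 years. Counting the 4 months from 29 June 2020, the latest 2020 date in the SAP (the access date of the source cited for the margin), gives late October 2020 and a gap of 4.1 years.

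**2. Secondary endpoints side by side.**

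| Protocol, Study end points | SAP, Secondary endpoints |
|---|---|
| Propofol to tube confirmation | Absent; induction time now runs from propofol to loss of twitch |
| Need for bag-mask ventilation, and its duration | Need kept, limited to induction; duration absent |
| Episode of SpO2 < 90% | Replaced by mean lowest SpO2, limited to induction |
| Provider-rated difficulty | Absent |
| (not listed) | First-attempt intubation |

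Induction time also appears in the protocol's procedures, as a further data point with a different definition (loss of spontaneous ventilation to tube placement).

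**3. The observation window.** The SAP defines induction as ending at loss of twitch. Both documents start TTI at loss of twitch and end it when end-tidal CO2 is confirmed. The two windows meet but do not overlap. As written, bag-mask ventilation or desaturation while the tube is being placed counts in neither SAP endpoint. The protocol's endpoints carry no such cut-off.

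**4. The plan's own sample size.** Inputs from the sizing text: difference 10 s, two-tailed 5%, power 80%. No SD is stated.

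n per arm = 2 × (z₀.₉₇₅ + z₀.₈₀)² × SD² / 10². With SD = 15 s: 2 × (1.960 + 0.842)² × 225 / 100 = 35.3, rounded up to 36. SDs of 14.94 to 15.14 s give exactly 36 by this formula (14.72 to 14.93 s with the t distribution). Then 36 / (1 − 0.20) = 45 per arm and 90 in total, which matches. SD 15 s is thus an assumption inferred from the sizing.

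**5. What the level changes.** Non-inferiority is shown when the observed difference is below 15 − t(1−α, 2n−2) × SD × √(2/n).

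For SD 15 s and n = 36, the standard error is 15 × √(2/36) = 3.54 s. One-sided 5%: 15 − 1.667 × 3.54 = 9.1 s. Upper limit of a two-sided 95% CI (one-sided 2.5%): 15 − 1.994 × 3.54 = 7.95 s, or about 8.0 s.

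| SD assumed | n per arm | Passes at one-sided 5% | Passes by 95% CI |
|---|---|---|---|
| 12 s | 36 | below 10.29 s | below 9.36 s |
| 15 s | 36 | below 9.11 s | below 7.95 s |
| 15 s | 45 | below 9.74 s | below 8.72 s |
| 25 s | 36 | below 5.18 s | below 3.25 s |

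At a true difference equal to the 15 s margin, where the false non-inferiority rate is greatest, that rate is 5% for the first rule and 2.5% for the second, whatever the SD.

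**The case against.** The strongest reply is that little here is new in 2024. The protocol's directional 15 s hypothesis is one-sided by construction, its sizing already names a 5% error rate, and the two-tailed wording belongs to a 10 s comparison, not to the non-inferiority test. On this view the SAP only makes the test explicit. That largely stands for sidedness. It does not settle the level, because the protocol never says which level applies to the non-inferiority test.

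A second reply is that November 2024 may be the date on which older text was compiled, since the SAP contains material dated April, May and June 2020. That is possible. Those dates attach to the sizing, the randomisation link and the margin's citation, however, and not to the test level or the secondary list.

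Third, the change in endpoints is partial. Need for bag-mask ventilation carries over, the protocol already planned to document further attempts after an unsuccessful one, and it names an induction time. All true. But first-attempt success was not a listed secondary endpoint, and induction time has a different start and end.

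Finally, a one-sided 5% test is a coherent rule, and no 2020 text sets 2.5% for non-inferiority. Replacing the SAP's rule now would itself be a late change. This stands, and the fix therefore keeps the SAP's test.

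**Conclusion.** The one-sided p < 0.05 level and the SAP's secondary list are not shown to be pre-specified. Separately, the SAP's bag-mask and saturation endpoints, as worded, miss the interval that TTI measures.

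The effect of the level alone is modest: about 1.2 s in the largest observed difference that passes (9.11 − 7.95), and 5% versus 2.5% in the maximum false non-inferiority rate. The first figure rests on an assumed SD of 15 s and 36 per arm. The risk of selective reporting from the changed secondary list cannot be quantified from the documents.

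A reader might infer two stronger things, and neither is supported.

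- **That the choices were made after the data were seen.** Actual enrolment, completion and data-access dates are not in the documents; the gap is measured against planned completion. The statement that data "will only be available to primary and co-investigators" is a confidentiality provision, not evidence of a look at results by arm.
- **That the 15 s margin is itself post hoc.** The SAP says "Our research team decided to use 15 s as non-inferiority margin", but the same margin and the direction of the hypothesis are in the protocol. The June 2020 access date of the cited source falls within the planned four months.

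**What to change.** 1. Analyse and report all four secondary endpoints in the protocol's Study end points as the planned set, without the loss-of-twitch cut-off. Label first-attempt success, lowest SpO2 and the redefined induction time as added in the SAP of 20 November 2024, and as post hoc unless an earlier dated document is cited. The protocol already provides for recording provider-rated difficulty, need for and duration of bag-mask ventilation, and SpO2 < 90% episodes. Time from propofol to tube confirmation is the SAP's induction time plus TTI for each patient, if end-tidal CO2 is taken as the confirmation.

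2. Report the box-minus-control difference in mean TTI with a two-sided 95% CI against the 15 s margin, alongside the planned one-sided 5% test, and say so if the two disagree. The SAP already plans 95% intervals for mean TTI in the two groups; this adds an explicit interval for the difference.

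The cost is SAP and report wording and a few extra or relabelled tables, with no new patients and, if the recording the protocol provides for was done, no new data. The downside is that some results become exploratory and a borderline primary result is reported less favourably.
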